1.7.8 Lumbar Disc Injection/Discography Risks and Complications

The complication rate of intravertebral disc injection is comparable to the complications associated with discography. The complications associated with discography are low, and is accepted to be less than 1%.

Although very unlikely, there is the potential that insertion of the spinal needle into the disc could damage adjacent visceral and/or neurologic structures as it is passed into the disc. Additionally, it is possible that the tip of the needle may not be placed into the nucleus pulposus of the disc. This could result in the product not being able to perform its intended function or impacting surrounding structures. This could lead to continued pain and functional deficit or even a worsening of symptoms. The potential for inadvertent damaging of surrounding structures and/or misplacing the product is minimized by the use of fluoroscopy to provide real time imaging of the placement and path of the needle. Furthermore, the use of trained and experienced physicians that routinely perform intra-discal procedures such a discography further reduces the likelihood of damaging adjacent structures and/or misplacing the product upon injection.

In a retrospective analysis of 10 discography studies in which prophylactic antibiotics were not given, an infection rate of 0.25% in 4891 subjects and 0.094% in 12,770 discs was found, with the conclusion that the risk of post-discography discitis was minimal. ⁴¹ The most serious and frequently encountered complication is discitis. One subject who received an injection of 6 million cells of rexlemestrocel-L experienced procedure-related discitis in Study MSB-DR001.

The incidence of infection can be decreased with the use of double needles and styleted needles. ^{42,43} Many practitioners prophylactically administer broad-spectrum antibiotics as a precaution against possible discitis. ^{44.47}

Nerve damage may also occur but usually causes only transient symptoms. Transthecal puncture may result in post-procedural headache. Other possible complications are needle breakage, accidental intra-dural injection, intrathecal hemorrhage, meningitis, arachnoiditis, osteomyelitis, and epidural abscess.

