6. STUDY PROCEDURE

6.1 Visit Schedule and Assessments

Table 3 shows all planned assessments, which are marked with an "X" for the visits at which they are performed. Subjects should be seen for all visits on the designated days or within the given windows for those visits. The study assessment schedule outlines all procedures to be performed on subjects at the scheduled visits.

In order to minimize variability in evaluations, ideally, the same personnel should perform the same tests and assessments on all the subjects at a given trial site, if possible.

Sites are required to access the interactive web response system (IWRS) at the beginning of the screening period to obtain a screening number. Sites are also required to access IWRS at the conclusion of the screening period to register the subject status. If the subject does not meet all inclusion and exclusion criteria, the subject will be considered a screen failure. If the subject meets all inclusion and exclusion criteria, the subject must be randomized a minimum of 7 days prior to treatment (Day 0) to allow time for shipment of investigational product to the site. In addition, treatment must be administered no later than 30 days following randomization.

Assessment	Screen/ Baseline ^b Visit 1 Days -105 to 0 ^a	Visit 2 Day 0 Treatment Injection ^w (7-30 days post- Randomiz ation)	Visit 3 1 Month (± 14 Days) ^a	Visit 4 3 Months (± 14 Days) ^a	Visit 5 6 Months (± 30 Days) ^a	Visit 6 12 Months (± 60 Days) ^a	Visit 7 18 Months (± 60 Days ^a	Visit 8 24 Months (± 60 Days ^a	Visit 9 36 Months (± 60 Days ^a	Unscheduled Visit ^c
Informed consent and privacy forms (e.g., HIPAA) ^d	Х	—	—	—	—					
Inclusion/exclusion criteria	Х	Х		_						
Demography and smoking history	X	_			_					
Medical & surgical histories	X				_					
Alcohol and Substance Abuse	X									
Questionnaire										
Mental Illness/Incompetence	Х									
Questionnaire										
Pain Catastrophizer Scale	Х									
SCORE or MORES assessment	X °									
Disease targeted, abbreviated PE e	Х	Х	Х	Х	X	X	Х	Х	Х	
Neurological Examination	Xf	X g	Х	Х	Х	Х	Х	Х	Х	Х
Targeted PE to rule out SI joint pain h	Х									
Vital signs, seated, if possible	Х	Xi	Х	Х	Х	Х	Х	Х	Х	Х
Height, weight, and BMI	Х	Х	Х	Х	Х	Х	Х	Х	Х	Х
Hematology	Х	—	Х	_	_	Х		Х	Х	
Chemistry Panel	Хj	—	Х	—	_	Х		Х	Х	
HIV	Х		_	_	_	_				
Pregnancy Test ^k	Х	X	_	_	_	_				
Flow Class I and II % PRA with specificity testing and DSA ¹	Х		—	—	—	Х		Х	Х	
MRI scan ^m	Х	_	_	_	_	Х	Х	Х	Х	

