- j. Screening Chemistry Panel includes: albumin, alkaline phosphatase, ALT, AST, BUN, creatinine, hsCRP, chloride, direct bilirubin, GGT, glucose, lactic dehydrogenase, sodium, potassium, phosphorous, total bilirubin, total calcium, carbon dioxide, total cholesterol, total protein and uric acid
- k. For women of child bearing potential. A serum pregnancy test will be analyzed by the central laboratory at screening. An additional urine pregnancy test will be performed prior to administration of study treatment to confirm a negative result. If the urine pregnancy test is positive, study treatment will not be administered that day, and the result will be confirmed by a serum pregnancy test.
- 1. Specificity testing and DSA only for those Class I or II PRA results \geq 5%. Specificity testing and DSA results will be blinded until the end of the study.
- m. MRIs and radiographs should be taken on the same machine using the same settings, and in accordance with the radiographic guidelines provided, from baseline to completion of the study to minimize potential differences in results caused by use of different machines. Radiographic evaluations may vary for a given subject depending on the time of day the assessments are made. Therefore, for each subject, all radiographic evaluations of a specific type (e.g., X-ray) should be taken at the same time of day at each assessment if possible, preferably in the morning. MRIs and radiographs will be evaluated by a core imaging provider for the criteria noted in the inclusion & exclusion criteria. All other radiographic evaluations at screening will be assessed by the investigator. Evaluation of the change in macromolecular content and hydration of the treated disc will be performed on a subset of subjects where T1 rho and T2 mapping capability is available.
- n. Screening DEXA scans and AP, lateral and flexion-extension x-rays performed according to study-defined procedure may be performed up to 6 months prior to procedure.
- o. Any female subject with a SCORE of ≥6 or male subjects with a MORES of ≥6 will require a lumbar spine DEXA scan to be performed. Similarly, subjects who are considered at risk, as defined in exclusion criterion #4 (Section 6.4.5), will be required to have a DEXA scan at screening, regardless of SCORE value.

Clinical Study Protocol Study MSB-DR003

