6.6.9 Laboratory Evaluations

Clinical laboratory tests will be performed according to the schedule indicated in Table 3. Specific laboratory parameters are displayed in Table 5.

Chemistry	Hematology	Special
Albumin	Hematocrit	hCG (urine)
Alkaline phosphatase (AP)	Hemoglobin	HIV
ALT (SGPT)	Red Blood Cells	anti-HLA class I and II antibody:
		Flow Class I and II % PRA
		(Specificity and DSA only for those
		Class I or II PRA results ≥5%)
AST (SGOT)	Platelets	hsCRP
CO2	White Blood Cells	Serum pregnancy test (beta hCG)
Blood urea nitrogen (BUN)	Neutrophils	
Calcium	Lymphocytes	
Chloride	Monocytes	
Creatinine	Eosinophils	
Direct Bilirubin	Basophils	
Total Bilirubin		
Glucose (non-fasting)		
Phosphorus		
Lactic dehydrogenase (LDH)		
Potassium		
Total Cholesterol		
Sodium		
Total protein		
GGT		
Uric Acid		

Table 5:	Laboratory Parameters

Any changes in clinical laboratory results deemed by the investigator to be clinically significant (see Section 7.5) or that qualifies as an adverse event should be documented.

All analyses, with the exception of urine pregnancy, will be performed at the central clinical laboratories.

Specificity testing and DSA results will be blinded until the end of the follow-up period.

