9.7.1 Primary Safety Endpoint

Evaluation of overall safety, which includes the following:

- Subject reported AEs and SAEs from baseline through 24 months post-treatment, including adverse events of special interest (i.e., AEs of worsening low back pain)
- Laboratory tests (hematology, serum chemistry, inflammatory markers and antibody analysis). Abnormal results will be assessed relative to normative ranges and shift tables from baseline through 24 months post-treatment
- Reported events from radiographic imaging from baseline through 24 months posttreatment, including disc height at the treated level
- Post-treatment interventions affecting the treated disc through Visit 8 (24 months posttreatment) (comparison of the proportion of subjects in each group with an adjudicated post-treatment intervention at the treated level, and the proportion of subjects in each group with an adjudicated post-treatment intervention any lumbar level)
- Vital signs (heart rate, blood pressure and temperature) and body measurements (height, weight and BMI)
- Physical examinations (abbreviated).
- Neurological examinations (motor, sensory, reflex).

[figure not shown]
Descriptive statistics will be used for the summary of safety parameters – the number and percentage will be used for the incidences of AE/SAEs, deaths, early discontinuation due to AEs, and post-treatment interventions. The AE/SAE severity and relationship with the study procedure and treatment will be summarized and presented.

The mean, standard deviation/error, minimum, median, and maximum will be used for the laboratory parameters. The shift table (cross-tabulation) for the changes from baseline (low/normal/high) for the laboratory parameters will also be also provided and the test for treatment difference.

[figure not shown]
Safety parameters of special interest (i.e., AEs of worsening low back pain) will be summarized through 24 months post-treatment by treatment arm, severity, and the time from the study injection to the start of the AEs (0 to \leq 7 days, >7 days to < 3 months, \geq 3 months to 24 Months).

The incidence of this special interest AE (worsening low back pain) occurring within 3 to 24 months after study treatment will be also summarized, by treatment arm, for the responders and non-responders of the Primary Efficacy Endpoint.

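### Inflammatory markers belong to the primary safety endpoint through 24 months, but the visible schedule requires hsCRP, the only such marker named as a test, at screening only

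*Combined protocol and SAP*

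**What the plan says.** The primary safety endpoint in section 9.7.1 includes "Laboratory tests (hematology, serum chemistry, inflammatory markers and antibody analysis", so inflammatory markers stand beside hematology, chemistry and antibodies as an item of their own. The same bullet sets the analysis: "Abnormal results will be assessed relative to normative ranges and shift tables from baseline through 24 months post-treatment". Later in 9.7.1 the protocol again plans shift tables for laboratory parameters, with a test for treatment difference.

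Section 6.6.9 says where timing and content come from. On timing: "Clinical laboratory tests will be performed according to the schedule indicated in Table 3". On content: "Specific laboratory parameters are displayed in Table 5".

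In Table 3 (section 6.1) the row "Chemistry Panel" is marked at screening and at Months 1, 12, 24 and 36. The screening mark carries footnote j, which reads "Screening Chemistry Panel includes: albumin, alkaline phosphatase, ALT, AST, BUN, creatinine, hsCRP, chloride" and continues with the remaining analytes. The later marks carry no footnote. No row is devoted to hsCRP.

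Table 5 has three columns: Chemistry, Hematology and Special. One of its rows runs "AST (SGOT) Platelets hsCRP", which places hsCRP in the Special column. Table 5 gives no visits. Apart from the abbreviation list, hsCRP is not mentioned elsewhere in the visible text.

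**The concern.** A shift table needs a baseline category and at least one post-baseline category for each subject. If hsCRP is measured only at screening, the second category does not exist, and a stated component of the primary safety endpoint is empty in all three arms.

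The item bears on risks that the protocol itself raises. Sections 1.7 and 1.7.4 name inflammatory response to allogeneic cells as a potential risk. Section 1.7.8 says of disc injection and discography: "The most serious and frequently encountered complication is discitis". Post-treatment MRI begins at Month 12, and section 7.2 labels low back pain within 14 days of the procedure as expected. A comparison of an inflammatory marker between arms is therefore a reasonable thing to have promised, and a visit that passes without the assay cannot be repeated.

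**Working it through.** No sample size, power or error-rate figure is involved. The check sets the passages side by side.

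**Step 1: which test could fill the item.** Section 9.7.1 lists hematology, serum chemistry and antibody analysis separately, so white cell counts (hematology) and % PRA (antibodies) already have their own places. Interleukin and TNF-α appear in the abbreviation list but not as study tests. That leaves hsCRP.

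**Step 2: is hsCRP part of the standard chemistry panel?** Compare footnote j with the Table 5 Chemistry column, treating total calcium and calcium, and carbon dioxide and CO2, as the same tests.
- Footnote j, screening panel: 21 analytes.
- Table 5, Chemistry column: 20 analytes.
- In footnote j but not in the Chemistry column: hsCRP, and nothing else.
- In the Chemistry column but not in footnote j: none.

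So 21 − 20 = 1, and that one is hsCRP. It is exactly what separates the panel that footnote j calls the screening panel from the one listed in Table 5.

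**Step 3: is hsCRP scheduled on its own?** Each other entry in the Special column has a Table 3 row.

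| Table 5 Special test | Own row in Table 3 | Visits marked |
|---|---|---|
| HIV | yes | screening |
| Pregnancy (serum, urine) | yes | screening, Day 0 |
| Anti-HLA % PRA | yes | screening, Months 12, 24, 36 |
| hsCRP | no | none, except through footnote j |

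**Step 4: do unscheduled visits fill the gap?** No. Footnote c does not list laboratory tests among the required assessments, and it exempts the pre-intervention visit from the chemistry panel.

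**Step 5: count.** Post-treatment chemistry visits within the 24-month window are Months 1, 12 and 24, which is 3. Visits at which the visible text requires hsCRP: 0 of 3, or 0 of 4 if Month 36 is counted. Pre-treatment measurements required: 1, at screening.

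**Step 6: the other reading.** If footnote j were meant for every chemistry visit, the count would be 3 of 3. The word limiting the footnote to screening would then be wrong, and Table 5 would have hsCRP in the wrong column. On either reading at least one passage must change.

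**The case against.** The absence is inferred. Nothing says hsCRP is dropped after treatment, and one row named for the chemistry panel, with the same contents at every visit, is a possible reading. Table 5 alone does not settle it either: footnote j runs hsCRP within the screening chemistry panel although Table 5 puts it under Special, so the column does not decide panel membership. Both points have force. But once Table 5 is set aside, the only text that puts hsCRP in any panel is footnote j, and its wording is confined to screening.

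Superscript placement is also weak evidence. Footnote y is attached at Visits 3 to 6 only, yet its text covers each post-treatment visit, and some superscripts in the extracted table are garbled. This is fair, and the point should not rest on where the letter sits. It rests on what footnote j says: y is worded broadly and j narrowly.

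Unseen material could resolve the gap. Safety text near 9.7.1 is blacked out, and a laboratory manual may list the assay. This stands as a limit on the conclusion. Against it, section 6.6.9 names Table 3 as the schedule.

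Section 1.7.4 says that immunogenic and inflammatory responses will be monitored through HLA antibody tests. That is a monitoring route, but 9.7.1 lists antibody analysis apart from inflammatory markers, and % PRA is not drawn after treatment until Month 12.

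A reader might infer that hsCRP is the only early laboratory signal of inflammation. The documents do not support this: hematology at Month 1 includes white cell and neutrophil counts, and that visit also has temperature, a neurological examination, X-rays and adverse event evaluation. What is missing is the dedicated marker that the endpoint names.

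A reader might also try to size the problem in discitis cases. Section 1.7.8 reports one case in MSB-DR001 and calls it procedure-related, while all three arms here receive a disc injection. One such event does not predict a difference between arms, and nothing in the documents says how well hsCRP would detect discitis.

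**Conclusion.** The point holds for the schedule as written. A named component of the primary safety endpoint has one required measurement before treatment and none at the three post-treatment chemistry visits through Month 24, so its shift table could not be filled from required data.

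The conclusion assumes that hsCRP is the intended marker, that footnote j means what it says, and that no redacted text or laboratory manual adds the test. It would go too far to say that no post-treatment hsCRP value will exist; the documents show only that none is required in the visible text. The defect is confined to one descriptive safety item. Hematology, chemistry and antibody summaries can still be produced, and the primary efficacy analysis is untouched. The sponsor should correct it because the choice is simple and a missed draw cannot be made up later.

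**What to change.** Reconcile Table 3, footnote j, Table 5 and section 9.7.1 so that they give one answer.

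- **Preferred:** require hsCRP at the existing post-treatment chemistry draws within the endpoint window, Visits 3, 6 and 8 (Months 1, 12 and 24). Give it its own Table 3 row, or reword footnote j to cover every chemistry visit, and align Table 5. Visit 9 (Month 36) is optional; it lies outside the 24-month endpoint and would serve only the longer follow-up. In 9.7.1, name hsCRP as the inflammatory marker.
- **Alternative:** if post-treatment hsCRP is not wanted, remove inflammatory markers from the shift-table endpoint in 9.7.1 and give the reason.
- **If a laboratory manual already schedules it:** carry those visits into Table 3.

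The preferred route costs one extra assay on blood already drawn, with no new visit, plus a protocol amendment, which under section 14 goes to the IRB/EC for approval. Subjects already past a visit will lack that value, so the report should state how many have an evaluable shift at each visit. The alternative needs only the amendment, but it gives up the comparison of the marker between arms.

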6.1.1 Screening Period

A subject will enter the screening period once a written informed consent has been signed by the subject. In addition, all subjects must sign a HIPAA authorization or other local regulatory agency required form as applicable for use, collection, and disclosure of PHI.

This initial screening period will not exceed 105 days (75 day screening period until randomization and a maximum of 30 days between randomization and study treatment). During the screening period it will be determined that the subject meets all inclusion and exclusion criteria. Baseline assessments will also be completed during this time. All patient-reported outcomes (including VAS and ODI assessments), as well as baseline use of pain medication (i.e., 2-week e-diary record), will be established during screening. All such assessments should be performed prior to the diagnostic disc injection to confirm intact annulus or discography, if deemed necessary. However, if the subject had received a previous diagnostic injection procedure to confirm intact annulus or discography prior to the screening period (but within the permitted timeframes to serve as the baseline evaluation; see Section 4.2.2), these patient-reported outcomes and e-diary entries must be started at least 14 days following the most recent injection procedure.

A neurological exam will be performed prior to the diagnostic injection to confirm an intact annulus or discography and again after the procedure. If a recent diagnostic injection or discography taken before the screening period serves as the baseline evaluation for a subject, the pre-injection neurological exam may be waived, though a neurological exam will need to be performed prior to any additional invasive procedures or the treatment injection. This neurological exam will be used as the subject's baseline neurologic status.

If a subject is re-screened, most patient-reported outcomes must be completed again at least 2 weeks after the most recent diagnostic injection procedure. These patient-reported outcomes include VAS assessments (leg and low back pain), ODI questionnaire, EQ-5D, and iPCQ. However, if an e-diary was collected during a previous screen, this may be used, provided it meets all criteria for a valid e-diary collection (i.e. 10 out of 14 days pain medication usage collected).

There must be at least a 2-week "washout" period following the diagnostic disc injection or discography prior to the injection of study treatment (see Section 6.4.8).

6.1.2 Randomization

Randomization must occur a minimum of 7 days prior to treatment (Day 0) to allow time for shipment of investigational product to the site. In addition, treatment must be administered no later than 30 days following randomization. Subjects will be enrolled in the study sequentially by dose via a central randomization system. Randomization will be stratified by site and by whether the subject is taking an opioid medication or not.

6.1.3 Safety and Efficacy Evaluation Period (Day 0 to 24 Months Post-treatment)

On Day 0/Treatment Administration day, each subject will receive an intradiscal injection of rexlemestrocel-L alone, rexlemestrocel-L +HA, or saline control in a 1:1:1 randomization ratio. This will commence the 24-month primary safety and efficacy period, which includes intensive safety and efficacy evaluations.

Treatment injection and post-procedure care (anesthesia, prophylactic antibiotics, blood product [i.e., packed red blood cells and platelets], rehabilitation regimens, etc.) will be performed in accordance with standard of care, as appropriate in the judgment of the investigator, and documented.

Subjects will be given the following directions for post-injection rehabilitation/treatment:

- Day of Procedure Bed Rest
- Day After Procedure Gentle Ambulation with gradual increase thereafter
- Days 1 to 3 Avoid repetitive bending, stooping and lifting greater than 10-15 lbs.
- Return to normal daily activity when pain has subsided to their baseline.

After the treatment injection visit, all safety and efficacy evaluations should be completed by blinded site staff.

Subjects will attend study visits 3, 4, 5, 6, 7, and 8 (corresponding to 1, 3, 6, 12, 18 and 24 months post-treatment) to complete the primary safety and efficacy period. Subjects will return at Study Visit 9 for a 36 month long-term safety and efficacy evaluation before completing the study. Subjects may also attend unscheduled visits for safety reasons as warranted.

If, for any reason, additional medication must be prescribed, subjects should inform the study site personnel.

Subjects may call the investigator at any time during the study if they experience any problems. The investigator may decide to follow up with a telephone call and/or request an unscheduled visit.

At least 2 blinded independent radiologists with a third radiologist to adjudicate any differences between two initial radiographic reviewers' assessments will review the specified screening radiographic images to confirm subjects meet the radiographic inclusion/exclusion criteria. Follow-up evaluation of radiographic images and any screening assessments that are not inclusion/exclusion criteria will be performed by at least 2 blinded independent radiologists with a third radiologist to adjudicate any differences between two initial radiographic reviewers' assessments as specified in Appendix 1.

Study center personnel (with the exception of unblinded staff preparing and administering the investigational treatment) and subjects will remain blinded to the treatment allocation for the entire 36-month post-treatment period. Blinded radiographic evaluators will also remain blinded for the entire post-treatment study period.

Treatment allocation for the primary analysis of safety and efficacy at 24 months post-treatment will occur only for the sponsor and any authorized representative. These personnel include those members of the study team responsible for generating a summary and analysis of the data. All site personnel, specifically those administering subject assessments and care, will be blinded to treatment allocation, with the following exceptions: unblinded CRAs (responsible for IP reconciliation) and unblinded statistician(s) (responsible for providing data for the interim analysis and DSMB data).

During Study MSB-DR003, subjects may attend unscheduled visits for safety reasons if warranted.

